## B. Statistical Considerations

### **Sample Size Justification and Analysis Plan**

[name], a biostatistician based in the CHB Clinical Research Program and affiliated with the Endocrinology Division, collaborated with us on the power calculations and statistical analysis plan.

Multiple testing. Although Aims 1 and 2 cover several hypotheses and measures, one endpoint is primary: blood flow in the NAcc at 4 hr after feeding. Our power analysis thus primarily focuses on two comparisons, embodied in Hypothesis 1 (Aim 1) and Hypothesis 5 (Aim 2). The remaining hypotheses concern secondary outcomes. We would not consider changing the sample size for the sake of detecting effects in these outcomes and have therefore not pursued power analyses for them. We will of course conduct rigorous statistical analysis on the secondary outcome variables and deduce whatever we can from the available data, but our resource planning is aimed above all at the question of 4-hr postprandial blood flow in the NAcc.

Power analysis. We view the design, illustrated in Fig. 1, as a crossover study with two experimental conditions (A: high GI, high insulin, normal glucose; C: high GI, low insulin, high glucose) and a common comparison condition (B: low GI, low insulin, normal glucose).

Our original analytic plan (alternative #1) calls for two pre-specified comparisons (A vs B and C vs B), conducted as if they were independent experiments, using 5% type I error for each comparison without adjustment for multiple testing. The assumption of independence may seem questionable because of the correlation among each subject's three observed outcomes —  $A + \delta + \epsilon_1$ ,  $B + \delta + \epsilon_2$ , and  $C + \delta + \epsilon_3$  under a random-effects or compound symmetry assumption, where A, B, and C are fixed means for the three conditions and  $\delta$  and  $\epsilon_i$  are independent Gaussian deviates — but this assumption is justified by the fact that the crossover analysis will hinge on two within-subject contrasts that are statistically independent:

$$\text{Cov}((A + \delta + \epsilon_1) - (B + \delta + \epsilon_2), (C + \delta + \epsilon_3) - (B + \delta + \epsilon_2)) = 0.$$

The detectable effect for each paired-sample comparison (A vs B or C vs B) is  $(t\alpha/2 + t\beta) \times \text{SD}(D)/n^{1/2}$ , where n is the sample size, SD(D) is the standard deviation of the intrasubject difference in mean flow between conditions, and t() are Student deviates for power  $1 - \beta$  and two-sided type I error  $\alpha$  with  $n - 1$  df. Our prior study yielded  $\text{SD}(D) = 20$  units of blood flow. For these calculations we take  $\alpha = 0.05$  and a conservative value of  $\text{SD}(D) = 30$ . The planned sample of  $n = 15$  gives us 80% power to detect an effect of  $(2.1448 + 0.868) \times 30/15^{1/2} = 23.3$  units, or 4.3% of the mean flow (548 units in the prior study), and 90% power to detect an effect of 4.9%. These figures are comfortably below the 7.9% observed in our prior study. We therefore believe that the present protocol is adequately powered to detect clinically significant effects.

A still more conservative analytic plan (alternative #2) would be to apply the Bonferroni correction, halving the type I error rate for each of the two pre-planned comparisons. With this change, making  $\alpha = 0.025$ , the detectable effects are 4.8% with 80% power and 5.4% with 90% power. These figures are negligibly different from the earlier results.

Finally (alternative #3), we have considered framing the analysis as a 3-group comparison (A vs B vs C) with the null hypothesis that all three conditions have equal mean. Pairwise comparisons would be pursued if and only if the hypothesis of three equal means was rejected. The type I error rate of 5% would be applied to the 3-group (2-df) hypothesis. The principle of closed testing enables us to use a  $p < 0.05$  criterion for the pairwise comparisons as well, should they be made, while preserving the family wise type I error rate at 5% for the overall procedure (Bender R, Lange S, J Clin Epidemiol 54:343, 2001; Marcus R et al., Biometrika 63:655, 1976). We conducted simulations of this plan, again assuming  $\text{SD}(D) = 30$  with  $n = 15$ , and taking account of within-subject correlation across conditions, which we varied between  $\rho = 0$  and  $\rho = 0.8$ . The detectable difference between condition A and the common comparison condition was similar to the figures cited above: 4.2-4.3% with 80% power, depending on  $\rho$ , and 4.8-5.0% with 90% power. Besides being relatively insensitive to the degree of within-subject correlation, these results held regardless of whether we assumed a null

effect for condition C or an effect equal in magnitude to that of condition A.

We conclude that our original analysis plan (alternative #1 above) is most satisfactory, having the advantage of simplicity as well as comparable inferential power to the more intricate strategies.

### **Data Analyses**

#### **Endpoints**

Primary endpoint: Blood flow to the NAcc, as quantified by ASL.

Secondary endpoints: Blood flow to other brain areas relevant to intake control, connectivity of brain areas of intake control, metabolic fuels, hormones, hunger ratings, metabolomic profiles, ad libitum food intake.

Effect modifiers: insulin levels, glucose levels, metabolic fuels, hormones, hunger ratings, daily insulin requirement

Analysis of imaging data will be performed within the Statistical Parametric Mapping (SPM5, Wellcome Department of Cognitive Neurology) statistical image analysis environment. The images will be converted to a standard naming convention using the OSIRIX DICOM viewer (<http://homepage.mac.com/rossetantoine/osirix/Index2.html>) and then converted into Nifti format with appropriate spatial information in image headers. Once in the appropriate format, CBF images will be realigned to the first CBF image and then all CBF images will be transformed to a standard anatomical space using the registration parameters derived from the SPM "Normalization" algorithm applied to the mean image and using the gray matter a priori template as the target image. Normalization will be performed using the more standard preserve concentration option, which is acceptable since we do not expect significant atrophic changes during the study. Subsequently, images will be smoothed with an 8 mm FWHM kernel in preparation for statistical analysis. Statistical analysis will be performed on a voxel by voxel basis within SPM using the ANOVA algorithms of the general linear model and the SPM derived correction for multiple comparisons. A false discovery rate (FDR) threshold of 0.05 will be employed. Cluster size thresholding will not be initially employed to avoid loss of the small hypothalamus, but modest cluster thresholding may be applied to improve sensitivity of cortical activity change measurements. In addition, regional analysis of targeted regions will be performed by applying the regions defined with the AAL atlas on the spatially normalized images. MRI data will be correlated with data from venous sampling and hunger ratings using ANOVA algorithms.

To address the primary and secondary hypotheses, we will employ methods appropriate to crossover trials. Hypotheses 1,2,4-8 will be tested by paired T-Test, controlling for baseline and meal order. Hypothesis 3 and 9 will be addressed by the Pearson correlation between brain activation parameters and calculated caloric intake. Secondary analyses of associations between brain activation, metabolic and psychophysical parameters will be performed using an ANOVA design. All tests will be conducted with a 5% Type I error rate. SAS software (Cary, NC) will be used for all computations.

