### **B1. PURPOSE OF PROTOCOL**

**Objective:** To disentangle the postprandial effects of blood glucose and insulin on brain activation in relation to a high glycemic index (GI) meal.

Patients with type 1 diabetes mellitus (T1DM) have elevated rates of dysregulated eating and obesity (1,2). We hypothesize that these phenomena are exacerbated by effects of insulin and downstream metabolites on brain areas involved in food craving; specifically the Nucleus Accumbens (NAcc). If true, high GI meals might trigger craving and overeating, as this diet is associated with higher insulin requirements. We will dissect the role of insulin vs. glucose in mediating brain activation in response to a high GI meal by applying high vs. low GI meals with optimal (euglycemic clamp) vs. matched (primed-variable infusion) insulin coverage.

**Aim 1: To examine the effects of insulin - in relation to a high GI meal - on brain activation and food intake in the early and late postprandial period.**

Hypotheses:

1. (Primary) In the late postprandial period (4 hrs postprandial), blood flow to the NAcc will be greater after a high vs low GI meal when differences in glycemia are prevented by insulin.
2. In the late postprandial period, functional connectivity of the NAcc and prefrontal and limbic areas of intake control will be higher after a high vs low GI meal when preventing differences in glycemia.
3. Subjective food craving and ad libitum food intake will be associated with NAcc blood flow and prefrontal-NAcc functional connectivity in the late postprandial period.
4. In the early postprandial period (1 hr postprandial), blood flow will be decreased in the hypothalamus in response to a high vs. low GI meal.

**Aim 2: To examine the effects of glucose - in relation to a high GI meal - on brain activation and food intake in the early and late postprandial period.**

Hypotheses:

5. In the late postprandial period, NAcc activation will not differ between the high and low GI meal when insulin exposure is matched, in spite of the resulting hyperglycemia.
6. In the late postprandial period, functional connectivity of the NAcc and prefrontal and limbic areas of intake control will be similar after a high vs low GI meal.
7. In the early postprandial period, hypothalamus blood flow will be lower after the high vs. low GI meal.

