### **5. Randomization**

In this crossover trial, 3 conditions will be administered in 2 different sequences. As statistical comparison will only be made between condition (a) and (b), and (b) and (c), never between (a) and (c), the 2 orders will be (a)->(b)->(c), or (c)->(b)->(a). Condition b will always be adjacent to one of its comparators, limiting intra-subject variability, and the order of the compared conditions will be random. A randomization list of intervention sequences will be generated by the Clinical Research Program (CRP) at Boston Children’s Hospital.

The study director will be supplied with a numbered log for assignment of sequential randomization numbers (RID) as participants are enrolled. This log will only contain the RID.

The randomization log will be given to the BIDMC GCRC nutrition core and not shown to any study staff. It will contain the RID, sequence of conditions and a letter-code for each condition, in which only condition b is identifiable (e.g. B, X and Y).

Participants are randomized the day before the first test-visit, after participation is confirmed by phone. As each participant is enrolled, the study director will enter the participant’s unique study ID into the log, next to the next open RID. The study director will then communicate this information to the BIDMC GCRC nutrition core. The BIDMC GCRC nutrition core will reveal the experimental condition to the study physician to allow assignment to the appropriate insulin paradigm. Meals will be prepared accordingly and are labeled with the RID only and no information on the experimental condition.

For data pre-processing, the date of the MRI images will be obscured to maintain the blind. Only the letter code (e.g. B, X and Y) for each condition will be revealed to allow for single-subject and group analyses of brain response. After completion of all statistical analyses, the study director will be unblinded to the nature of the dietary intervention. If a participant withdraws before supplying usable data, the subject’s RID will not be reused or assigned to another enrollee. If a participant withdraws after one test-visit, available data will be analyzed but not included in the group analysis. If a participant withdraws after two test-visits, available data will allow for full analysis of one experiment and will be included in the group analysis. The randomization list will be slightly longer than needed in order to allow for such extra entries.

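### Hypothesis 5 predicts no late-period difference between conditions c and b, but it is tested and powered only as a difference, and no rule says how a non-significant result will be read

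*Combined protocol and SAP*

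**What the plan says.** Section B1 (Purpose of Protocol) states two null predictions for the late postprandial period under Aim 2. Hypothesis 5 is that "NAcc activation will not differ between the high and low GI meal when insulin exposure is matched, in spite of the resulting hyperglycemia". Hypothesis 6 is that "functional connectivity of the NAcc and prefrontal and limbic areas of intake control will be similar after a high vs low GI meal".

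The Data Analyses section assigns both to the same method as the hypotheses that predict a difference: "Hypotheses 1,2,4-8 will be tested by paired T-Test, controlling for baseline and meal order". The only decision criterion there is a 5% type I error rate.

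Under Sample Size Justification and Analysis Plan, Hypothesis 5 is placed beside Hypothesis 1: "Our power analysis thus primarily focuses on two comparisons, embodied in Hypothesis 1 (Aim 1) and Hypothesis 5 (Aim 2". The chosen plan (alternative #1) makes two comparisons, A vs B and C vs B, "using 5% type I error for each comparison without adjustment for multiple testing". The calculation gives a detectable effect for each comparison and concludes: "We therefore believe that the present protocol is adequately powered to detect clinically significant effects". Hypothesis 6 falls among the secondary outcomes, for which the plan says it did no power analysis.

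**The concern.** For Hypothesis 5 the predicted result is the null hypothesis of the planned test. A significant result would count against the prediction. A non-significant result could mean that the conditions are close, or only that the data are too noisy to separate them. The noisier the data, the more often the predicted result appears.

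The power statement does not fill the gap. Power of 80% to reject equality at a given true difference is not the chance of supporting Hypothesis 5 when it is true. The simulations for alternative #3 do not fill it either: a null effect of condition C appears there only as a scenario when computing the detectable effect of condition A.

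Section B1 sets out to separate the effects of glucose and insulin, and c versus b is the only planned contrast that varies glucose with insulin matched. If it is non-significant, a reader will be inclined to conclude that glucose does not contribute in the late period. The plan neither supports that conclusion nor guards against it.

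**Working it through.** **Inputs from the Sample Size section:** n = 15; SD(D) = 30 (called conservative) or 20 (prior study); two-sided alpha 0.05; mean flow 548 units; prior-study effect 7.9%, which is 0.079 × 548 = 43.3 units. The documents give no equivalence margin, so every margin below is illustrative.

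**1. The plan's own figure.** SE = 30/√15 = 7.746. At 80% power, (2.1448 + 0.868) × 7.746 = 23.3 units, or 4.3% of 548. At 90% power, (2.1448 + 1.345) × 7.746 = 27.0 units, or 4.9%. Both reproduce. Both are power to reject equality.

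**2. What a non-significant c minus b leaves open.** The half-width of the confidence interval is t × SD/√15, with t(0.975, 14) = 2.1448 and t(0.95, 14) = 1.761.

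| | SD 30 | SD 20 |
|---|---|---|
| 95% CI half-width | 16.6 units (3.0%) | 11.1 units (2.0%) |
| 90% CI half-width | 13.6 units (2.5%) | 9.1 units (1.7%) |

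**3. Chance that c minus b is non-significant.** Noncentral t, 14 df, noncentrality = true difference/SE (for example 11.65/7.746 = 1.50).

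| True difference | SD 30 | SD 20 |
|---|---|---|
| 11.65 units (2.1%) | 71% | 44% |
| 16 units (2.9%) | 51% | 18% |
| 23.3 units (4.3%) | 20% | 1.3% |
| 43.3 units (7.9%) | 0.06% | about 0 |

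**4. Chance of supporting Hypothesis 5 under an explicit rule.** The rule is: test non-significant AND 90% CI inside ±m. That is |mean| < 2.1448·s/√15 and |mean| + 1.761·s/√15 < m, where s is the observed SD. It was evaluated by simulating the mean and the variance. Because the rule also requires non-significance at 5%, support cannot exceed 95% when the true difference is 0.

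| Margin m | True difference | SD 30 | SD 20 |
|---|---|---|---|
| 27 units (4.9%) | 0 | 88% | 95% |
| 23.3 units (4.3%) | 0 | 77% | 95% |
| 21.65 units (half of 43.3) | 0 | 68% | 94% |
| 16.44 units (3% of 548) | 0 | 31% | 82% |
| 23.3 units | 5 | 68% | 84% |

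**5. What the rule changes, at a margin of 23.3.** The first figure is the chance of a no-glucose-effect reading from non-significance alone; the second is the chance under the rule.

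| True difference | SD 30 | SD 20 |
|---|---|---|
| 23.3 units | 20% → 4.4% | 1.3% → 0.9% |
| 11.65 units | 71% → 40% | 44% → 42% |

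With a true difference of 0 and the same margin, the result is inconclusive (non-significant, interval not inside) in about 18% of trials at SD 30 and 0.3% at SD 20.

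These figures use the plan's own unadjusted formula with n − 1 df and assume no dropout. Using 13 or 12 df for meal order and baseline moves the 95% half-width at SD 30 from 16.6 to 16.7 or 16.9, before any variance reduction from the baseline adjustment.

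**The case against.** The strongest reply is that the harm is inferred. A reader might take the plan to intend non-significance as proof of no glucose effect. No passage says so: the hypotheses state expectations, and the analysis section says only how the contrast is tested. The paired analysis also yields an estimate and standard error, so an interval could be reported anyway. This stands, and it limits the charge to a missing reading rule. It does not remove the charge, because a margin chosen after the results are seen carries little weight.

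A reader might also infer that the trial's main conclusion fails. It does not. Only Hypothesis 1 is labelled primary in B1, and it predicts a difference, which the t-test suits. The possibility in Section 2.5 that craving persists despite optimal insulin coverage rests on a versus b.

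Nor do the documents show that the power arithmetic is wrong or mislabelled, or that 15 participants are too few. The figures reproduce and are described as power to detect an effect, and support for Hypothesis 5 is attainable at moderate margins. What is missing is any figure for the chance of supporting it.

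Two further points stand. Hypothesis 6 is secondary and deliberately unpowered, so only the reading of its result is at issue. And a margin is not the only remedy: declining to read non-significance as no difference, and reporting the interval, would prevent the error, though Hypothesis 5 could then not be claimed as supported.

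**Conclusion.** The point holds, and should be fixed. The test assigned to Hypothesis 5 can refute it but cannot support it; the stated power answers a different question; and nothing says how a non-significant c minus b will be read. The exposure is to small and moderate glucose effects, and it is larger at the SD of 30 on which the plan relies than at the prior study's 20. An effect as large as the prior study's would not be missed at either SD. The non-significance figures rest on the plan's n, SD and formula. The figures for supporting Hypothesis 5 also rest on assumed margins. Hypothesis 6 shares the problem of interpretation, but the documents give no variance from which to size it.

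**What to change.** **Data Analyses section.** Report c minus b at 4 hours with its confidence interval, and state that non-significance alone will not be read as no difference. To claim support for Hypothesis 5, require the 90% interval to lie inside a margin that the sponsor fixes and justifies before the letter codes are released. State the readings:

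- non-significant, interval inside the margin: supports Hypothesis 5;
- non-significant, interval not inside: inconclusive;
- significant, interval inside: a difference smaller than the margin, not an absence of difference.

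For Hypothesis 6, report the estimate with its interval and make no similarity claim from non-significance.

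**Masking.** The Randomization section provides "a letter-code for each condition, in which only condition b is identifiable (e.g. B, X and Y", and adds: "After completion of all statistical analyses, the study director will be unblinded to the nature of the dietary intervention". To keep this, compute the same test and 90% interval for X − B and Y − B, and apply the Hypothesis 5 rule to c minus b after unblinding.

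**Sample Size section.** Say that the existing 80% and 90% figures do not give the power to support Hypothesis 5. Add the chance of support under the rule actually adopted, at SD 30 and SD 20, with at least one non-zero true difference.

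**Cost.** Added wording and one interval per contrast, with no added enrolment and no change to Hypothesis 1. The stated power for Hypothesis 5 will be lower, markedly so at a tight margin if the SD is 30, and some trials will end inconclusive. A wide margin protects little against small effects; a tighter one protects more but costs power. The sponsor has to justify that trade-off.

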**3.3.2. Primed-variable insulin infusion - experimental condition c (figure 1)**

In the run-in period, glucose levels will be measured every 5 minutes. A basal insulin infusion will be initially administered at 80% of the patients insulin pump basal rate, and will be adjusted between 0.1 and 2.5 mU/kg·min, depending upon the patient’s plasma glucose level in relation to the target range target of 90-100 mg/dl. Once steady state is achieved, baseline laboratory studies and imaging will be obtained and test meal administered. Then, a primed-variable infusion of insulin will be administered at the rate established during the pre-test visit to achieve similar plasma insulin levels. For patient safety, glucose levels will be measured every 30 minutes. If glucose levels are > 400 mg/dl or < 60 mg/dl, insulin infusion will be adjusted to maintain glucose levels target of 60-400 mg/dl. Insulin infusion will continue for 4 1/2 hours postprandial. Then, Insulin infusion will be discontinued and insulin pump therapy resumed according to the participants’ home regimen using their own equipment.

[figure not shown]

Figure 1:

**Figure 1: Schematic depiction of anticipated glycemic changes and insulin levels during the different experimental conditions.** Theoretical glycemic response to the meal is plotted in gray, anticipated insulin requirements in blue and resulting blood glucose in green. (a) High GI meal with euglycemic clamp, (b) low GI meal with euglycemic clamp, (c) high GI meal with primed-variable insulin infusion at the rate established during the pre-test visit. As the high GI meal is associated with higher insulin requirement, this condition will result in moderate hyperglycemia. Thus, the design will allow comparison between a high and low GI meal with matched blood glucose but different insulin levels (experiment 1 - condition a vs. b) **or** matched insulin with different blood glucose levels (experiment 2 - condition b vs. c)

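### Hypotheses 3 and 9 are the same sentence and share one Pearson correlation with no condition or within-man contrast, so the test does not isolate the insulin or the glucose effect

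*Combined protocol and SAP*

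**What the plan says.** Section B1 states two aims. The first is "Aim 1: To examine the effects of insulin - in relation to a high GI meal - on brain activation and food intake"; the second is "Aim 2: To examine the effects of glucose - in relation to a high GI meal - on brain activation and food intake". Hypothesis 3, under the first, and Hypothesis 9, under the second, read identically: "Subjective food craving and ad libitum food intake will be associated with NAcc blood flow and prefrontal-NAcc functional connectivity in the late postprandial period". Neither names a condition, a contrast or a direction.

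Under Data Analyses, one sentence covers both: "Hypothesis 3 and 9 will be addressed by the Pearson correlation between brain activation parameters and calculated caloric intake". The other hypotheses are treated differently: "Hypotheses 1,2,4-8 will be tested by paired T-Test, controlling for baseline and meal order".

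The legend to Figure 1 in section 3.3.2 says what separates the two exposures. Insulin is isolated by "matched blood glucose but different insulin levels (experiment 1 - condition a vs. b"), and glucose by "matched insulin with different blood glucose levels (experiment 2 - condition b vs. c"). Section 2.2 says the same. Neither place ties Hypothesis 3 to the first experiment or Hypothesis 9 to the second.

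**The concern.** Hypotheses 3 and 9 are the only numbered hypotheses that link the brain response to eating, and each is filed under a different exposure. The design can separate the exposures only through the within-man contrasts a-b and c-b. The planned correlation is attached to neither.

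The plan also leaves open whether levels or between-condition differences are correlated, and how several visits from one man are handled. On the plain reading, levels are correlated. Differences between men that have nothing to do with the meal or the infusion then enter the coefficient. A significant result could be entered under both aims without showing that insulin or glucose has anything to do with intake.

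**Working it through.** **The plan's own figure.** The Power analysis gives (2.1448 + 0.868) × 30/√15 = 23.3 units, and 23.3/548 = 4.3% of mean flow. This reproduces (23.34 units, 4.26%). It concerns the primary endpoint. The plan gives no power figure for Hypotheses 3 and 9 and says it did not calculate power for secondary outcomes.

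**Inputs.** From the documents: n = 15, three conditions, 5% error per test, two-sided as in the Power analysis. Alternative #3 there varies the within-subject correlation ρ from 0 to 0.8 for blood flow. Using the same ρ for food intake is an assumption. Simulations use 40,000 trials per setting, compound symmetry and unit variance.

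**1. All visits pooled.** Hypotheses 3 and 9 are then one coefficient with one p-value. If the 15 × 3 = 45 visits are treated as independent and there is no true association, the simulated error rate is 5% at ρ = 0, 9% at 0.4 and 21% at 0.8.

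**2. Split into a/b and b/c, one mean per man.** Suppose a stable trait, fully shared by flow and intake, is the only link, and neither exposure has an effect.
- The true correlation of two-visit means is ρ / [(1 + ρ)/2] = 2ρ/(1 + ρ).
- At ρ = 0.4 this is 0.8/1.4 = 0.57; at ρ = 0.8 it is 1.6/1.8 = 0.89. The critical value for 15 pairs is 0.514.
- In simulation both hypotheses are significant in 48% of trials (ρ = 0.4) and 99.7% (ρ = 0.8).
- With a-b and c-b differences the trait cancels, and both are significant in 0.4%.

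**3. Split, with the visits stacked as 30 points.** Suppose instead that condition a raises both flow and intake by the same amount in every man, with no other link. Share of trials significant:

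| Shift (SD) | a+b, ρ = 0 | b+c, ρ = 0 | a+b, ρ = 0.8 | b+c, ρ = 0.8 |
|---|---|---|---|---|
| 1 | 19% | 5% | 24% | 13% |
| 1.5 | 54% | 5% | 57% | 13% |
| 2 | 88% | 5% | 89% | 13% |

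The stacked coefficient therefore does respond to an insulin shift. Pooling all three conditions does not discriminate: at ρ = 0 an insulin-only and a glucose-only shift each give about 23%, 65% and 95%.

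**4. Shared condition b.** Under the null, the two coefficients correlate roughly as the square of the correlation between their inputs.
- Visit means: the input correlation is (1 + 3ρ)/[2(1 + ρ)] = 0.50, 0.79 and 0.94 at ρ = 0, 0.4 and 0.8. The squares are 0.25, 0.62 and 0.89 (simulated 0.24, 0.60, 0.88).
- Differences: the input correlation is (1 − ρ)/[2(1 − ρ)] = 0.5 at any ρ, squared 0.25 (simulated about 0.24).
- The Power analysis sets the covariance of the two contrasts to zero. Both contain the same condition b error, so under its own model the covariance equals the variance of that error.
- With visit means, given a false positive for Hypothesis 3, Hypothesis 9 is also significant in the same direction 7%, 23% and 53% of the time. The unconditional chance of the double false positive is about 0.3%, 1.1% and 2.7%.

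**5. Power of a difference correlation.** Detectable r at 80% power with 15 men: tanh[(1.960 + 0.842)/√12] = tanh(0.809) = 0.67. A shift common to all men is subtracted out with the mean, so this test is significant in only 5% of trials in each of the shift scenarios of step 3.

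**The case against.** The strongest reply is that the split is implied. Section 3.3.2 labels experiments 1 and 2. Section 5 restricts comparisons to a with b and b with c, and says two visits can complete one experiment. The Power analysis says the crossover analysis rests on two within-subject contrasts, and Data Analyses promises methods suited to a crossover. On that view Hypothesis 3 is one association tested in a/b, and Hypothesis 9 the same association tested in b/c. This is a fair inference, but no section states it, and the Pearson sentence differs from the paired tests named beside it. Even if accepted, it does not settle whether levels or differences are used.

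A reader might also infer that the planned coefficient cannot bear on either aim. That goes too far: step 3 shows that a stacked a+b correlation picks up an insulin shift. What stands is that it mixes the shift with differences between men and so does not isolate the contrast.

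The plan also lists "Effect modifiers: insulin levels, glucose levels, metabolic fuels, hormones, hunger ratings, daily insulin requirement" and mentions secondary ANOVA association analyses. These might give exploratory information, but neither is linked to Hypothesis 3 or 9, and the ANOVA is not specified.

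Finally, difference correlations have a real cost: they miss an effect common to all men. That objection stands, and the fix must answer it.

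**Conclusion.** The point holds. The identical wording and the single test without conditions are facts of the text. Run literally, one result serves both aims. Run by experiment on levels, a stable link between men can produce significance under both aims when neither exposure matters. The 48% to 99.7% figures assume one trait fully shared by flow and intake and ρ of 0.4 to 0.8 in both; a weaker trait would give less. The error rates of 9% and 21% apply only if 45 visits are treated as independent. At ρ = 0 there is no inflation.

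Three stronger readings are not supported. The documents do not say that one result will be reported twice or counted as two confirmations; the wording merely permits it. The conditional 53% is not the chance of a double false positive, which is about 2.7% at most over the range examined. And the separation of insulin from glucose in the trial's main question is not undermined: it rests on Hypotheses 1 and 5, which have paired comparisons. Hypotheses 3 and 9 are secondary, and the sample size does not depend on them.

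**What to change.** Reword Hypotheses 3 and 9 and the Pearson sentence as follows.

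- **Hypothesis 3 (experiment 1, conditions a and b):** correlate each man's a-b difference in 4-hour NAcc flow, and in prefrontal-NAcc connectivity, with his a-b difference in ad libitum kcal.
- **Hypothesis 9 (experiment 2, conditions b and c):** the same with c-b differences. Another analysis of the within-man association, such as a mixed model with a condition interaction, would also serve if specified in advance.
- State that the two tests share condition b and are not independent confirmations.
- Report any correlation pooled over all visits once, as descriptive, and credit it to neither aim.
- Report the mean a-b and c-b differences in flow and intake alongside, because a difference correlation cannot show a shift common to all men.

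Both hypotheses also name subjective craving, which the Pearson sentence omits; the revised text should say how it is handled.

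The cost is wording; no new data are needed. The revised plan should state that with 15 men only r of about 0.67 has 80% power, and that differences give up the information between men. A null result would therefore say little.
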